**Table 3 – Additional Evaluations**

Parameter	Definition
-----------	------------

Total RF ablation time	Total RF ablation time as measured by total time of ablation lesion applications will be documented. These values will be compared between the FIRM-guided and conventional ablation groups. If ablation for AT/atrial flutter is pursued, this ablation time will be documented separately
Total radiation exposure	As above, these values will be compared between the FIRM-guided and PVI groups.
Repeat procedure and hospitalization	Any information regarding repeat procedures and re-hospitalizations will be collected and compared between groups
Quality of Life	Impact on quality of life, using patient-reported outcome instruments (EQ-5D and AFEQT), within treatment groups (change from pre-procedure to post-procedure follow-up timepoints) and between treatment groups. Analysis will be performed if primary endpoints are met.
Economic Analysis	Cost-effectiveness analysis based on clinical and patient-reported outcomes and resource utilization. Analysis will be performed if primary endpoints are met.

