- Neurological Exam (if clinically indicated) if symptoms suggestive of neurologic disease, and is to be performed by the neurology medical staff.
- Prior to the procedure, anticoagulation therapy will be performed as per institutional standard.
- EQ-5D and AFEQT Quality of Life survey.

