#### E. *Additional Follow-up*

Subjects will be asked to complete the EQ-5D survey monthly, starting at 1 month post-procedure through the 12-month follow up period. The frequency of survey completion may be changed if inadequate patient compliance is observed.

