#### ***1.2.1.5.3 Quality of Life***

Impact on quality of life, using patient-reported outcome instruments (EQ-5D and AFEQT), within treatment groups (change from pre-procedure to post-procedure follow-up timepoints) and between treatment groups. Analysis will be performed if primary endpoints are met.

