#### 2.3 Additional Secondary Investigations

Secondary Endpoints (unpowered) include:

1. AF termination or CL prolongation, as identified by:

- a. Termination of spontaneous or induced AF by ablation of the source of arrhythmia.
- b. Reduction of the mean AF rate by at least 10% by ablation of the source of arrhythmia.
- 2. Single-procedure freedom from AF recurrence from 3-12 months post index ablation procedure (with 90-day blanking period) (Long-Term Effectiveness).
- 3. Freedom from symptomatic AF/AT recurrence from 3-12 months post index ablation procedure (with 90-day blanking period).
- 4. Freedom from AF recurrence from 0 – 12 months post index ablation procedure (without 90-day blanking period) (Long-Term Effectiveness).
- 5. Freedom from AF recurrence at 12 months post index ablation procedure (can include repeat procedures) (Long-Term Effectiveness).

Additional Investigations (unpowered) include:

- 1. Total RF ablation time.
- 2. Total Radiation Exposure.
- 3. Repeat ablation procedure and associated hospitalizations.
- 4. Quality of Life, as measured by the EQ-5D and AFEQT.
- 5. Cost-effectiveness analysis.

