### **3 Tables, Listings, and Figures**

#### **3.1 Tables**

- 3.1.1 Summary of Demographic Characteristics by Treatment Group**
- 3.1.2 Summary of Index Ablation Procedure by Treatment Group**
- 3.1.3 Summary of Acute Effectiveness by Treatment Group**
- 3.1.4 Summary of Long-Term Effectiveness by Treatment Group**
- 3.1.5 Summary of Acute Adverse Events by Treatment Group**
- 3.1.6 Summary of All Adverse Events by Treatment Group**
- 3.1.7 Summary of Acute Serious Adverse Events by Treatment Group**
- 3.1.8 Summary of Change From Baseline of EQ5D Quality of Life Scale by Treatment Group**

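### The between-arm quality-of-life comparison has no stated estimator and by default reads as unadjusted change scores; adjusting for the baseline score already collected is a small, free gain in precision

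*Protocol*

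**What the plan says.** Protocol Table 3 (Additional Evaluations) says that EQ-5D and AFEQT will be assessed "within treatment groups (change from pre-procedure to post-procedure follow-up timepoints) and between treatment groups". SAP 1.2.1.5.3 repeats the sentence, beginning "Impact on quality of life, using patient-reported outcome instruments (EQ-5D and AFEQT), within treatment groups", and adds no model, test, covariate or main time point. In SAP 3.1 the only quality-of-life table is 3.1.8, "Summary of Change From Baseline of EQ5D Quality of Life Scale by Treatment Group". The only quality-of-life listing, SAP 3.2.5, also covers EQ-5D alone.

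Both scales are measured before treatment: Protocol 9.1 B lists "EQ-5D and AFEQT Quality of Life survey" among the baseline assessments. The Schedule of Assessments (Protocol Table 4) has both again at 3, 6 and 12 months. EQ-5D also has a monthly schedule in Protocol 9.3 E: "Subjects will be asked to complete the EQ-5D survey monthly, starting at 1 month post-procedure through the 12-month follow up period". The same paragraph allows that "The frequency of survey completion may be changed if inadequate patient compliance is observed".

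On status, SAP 2.3 places quality of life in the list headed "Additional Investigations (unpowered) include", and Protocol Table 3 adds "Analysis will be performed if primary endpoints are met". It is nevertheless one of the two topics of the secondary objective (Protocol 4, SAP 1.1.2), and SAP 1.2.1.5.3 stands under the secondary outcomes.

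**The concern.** The main endpoints each have a named method: Kaplan-Meier estimation for the long-term endpoints, a chi-square test for the acute ones, and Cox or Cochran-Mantel-Haenszel analyses for centre effects (SAP 2.2 and 2.6). Quality of life has none. A programmer following the text and the table list would produce mean change from baseline by arm and compare the means.

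That comparison is valid under randomisation but usually less precise than it could be. A change score subtracts the whole baseline value, that is, it fixes the baseline coefficient at 1. When the baseline predicts follow-up with a slope below 1, this over-corrects and adds noise. Regressing follow-up on baseline lets the data set the coefficient, and it also deals properly with chance baseline imbalance.

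Within-arm change, the only analysis for which a quantity is spelled out, does not compare the two procedures. What is at stake is the width of the interval for a patient-reported comparison that will be reported, and that feeds the cost-effectiveness analysis, if the primary endpoints are met.

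**Working it through.** **Inputs from the documents.** Baseline scores on both scales; 1:1 randomisation (Protocol 5.2); 77 evaluable subjects per arm (Protocol 15.3, SAP 2.4). No standard deviation, correlation, effect size or power is given for quality of life, so there is no quality-of-life figure to reproduce.

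The 77 belongs to the primary endpoint. It reproduces with success rates 0.50 and 0.55, margin 0.15, one-sided 5% and 80% power: (1.645 + 0.842)² × (0.25 + 0.2475) / 0.20² = 76.9, so 77. It is used below only as an illustrative number per arm.

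**Assumed inputs.** Correlation ρ between baseline and follow-up score: 0.3, 0.5, 0.7. Ratio k of follow-up SD to baseline SD: 1 first, then 0.7 and 1.3.

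**Formulas.** With the baseline SD as the unit and the same number per arm, the variance of the between-arm difference is proportional to:
- change score: 1 + k² − 2ρk, which is 2(1 − ρ) when k = 1
- baseline-adjusted (ANCOVA): k²(1 − ρ²), which is 1 − ρ² when k = 1
- follow-up score alone: k², which is 1 when k = 1

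The ratio of the first to the second equals 1 + (1 − ρk)² / [k²(1 − ρ²)]. It is never below 1, and it equals 1 only when the slope ρk is exactly 1. With k = 1 it reduces to 2/(1 + ρ).

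**Equal SDs (k = 1).**

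| ρ | Change 2(1−ρ) | ANCOVA 1−ρ² | Variance ratio | SE ratio | Variance removed by ANCOVA |
|---|---|---|---|---|---|
| 0.3 | 1.40 | 0.91 | 1.54 | 1.24 | 35% |
| 0.5 | 1.00 | 0.75 | 1.33 | 1.15 | 25% |
| 0.7 | 0.60 | 0.51 | 1.18 | 1.085 | 15% |

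At ρ = 0.9 the variance ratio is 2/1.9 = 1.05 and the SE ratio 1.026, so the gain nearly vanishes.

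**Check by simulation.** With normal scores, 77 per arm and 4,000 replicates, the variance ratios were 1.51, 1.31 and 1.16, and the SE ratios 1.23, 1.14 and 1.08. They lie slightly below the large-sample values, which is in keeping with the small cost of estimating the slope plus simulation error.

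**Unequal SDs, ρ = 0.5.**
- k = 0.7: (1 + 0.49 − 0.70) / (0.49 × 0.75) = 0.79 / 0.3675 = 2.15, an excess of 115%
- k = 1.3: (1 + 1.69 − 1.30) / (1.69 × 0.75) = 1.39 / 1.2675 = 1.10, an excess of 10%

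**What this means at 77 per arm (k = 1).** The detectable difference at 80% power and two-sided 5%, in SD units, is 2.802 × √(2/77) = 0.4515 times the square root of the variance factor.
- Change scores: 0.53, 0.45, 0.35 for ρ = 0.3, 0.5, 0.7
- ANCOVA: 0.43, 0.39, 0.32

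Equivalently, 77 per arm with adjustment is worth 77/0.65 = 118, 77/0.75 = 103 or 77/0.85 = 91 per arm with change scores.

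**The other simple default.** If the open wording led someone to compare follow-up scores alone, the variance would exceed ANCOVA's by the factor 1/(1 − ρ²): 1.10, 1.33 and 1.96. Neither unadjusted choice is better than adjustment in large samples.

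**The case against.** The strongest objection is that the plan never says the arms will be compared on raw change. In the shared sentence the bracketed reference to change follows the within-group analysis, and the between-group part carries no method. Table 3.1.8 is only the title of a descriptive summary. A baseline-adjusted comparison would be compatible with both. This stands: a reader might infer that the sponsor has committed to an inefficient estimator, and the text does not support that. What remains is that change is the only quantity named, no adjustment is mentioned anywhere, and the method is open to choice after the data are seen.

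Four further readings go too far.
- A reader might say that change scores throw the baseline away. They use it, with a fixed coefficient.
- A reader might take 15% to 35% as the excess noise. Those figures are the share of variance that adjustment removes at ρ from 0.7 to 0.3; the excess is 18% to 54% in variance, or 8.5% to 24% in standard error.
- A reader might argue that improvement in both arms will be regression to the mean misread as efficacy. Entry is selected on documented AF episodes, not on a quality-of-life score, both arms receive active ablation, and nothing in the documents says that within-arm change will be taken as evidence of effect. The narrower point holds: within-arm change does not compare the arms.
- A reader might conclude that AFEQT will not be analysed. SAP 1.2.1.5.3 and 2.3 both name it; only its table and listing are absent.

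It is also fair to say that a repeated-measures model is a preference. ANCOVA at one named visit would serve, and centre terms for up to 15 or 20 sites would cost degrees of freedom in a trial of 170.

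**Conclusion.** The point holds as a minor, free improvement. As written, the plan leads by default to unadjusted change scores by arm, while the data for a comparison that is at least as precise are already being collected. With equal SDs and ρ of 0.3, 0.5 and 0.7, the avoidable excess is about 54%, 33% and 18% in variance. These sizes rest wholly on assumed values: at ρ = 0.5 the excess runs from about 10% to 115% as the follow-up SD goes from 1.3 to 0.7 times the baseline SD. The direction does not depend on those values, given randomisation and a reasonably large sample.

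Because quality of life is unpowered and its analysis is conditional on the primary endpoints, no sample size, primary conclusion or safety conclusion changes. Its place in the secondary objective does not make this a serious defect, since no decision rule is attached to it.

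**What to change.** In Protocol Table 3 and SAP 1.2.1.5.3, state that the between-arm comparison of AFEQT and of EQ-5D is adjusted for the baseline score of the same scale. Either of two forms will do:
- ANCOVA at 12 months; or
- a repeated-measures model over the 3, 6 and 12 month visits, with treatment, visit, their interaction and the baseline score, and 12 months as the main contrast.

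The second uses all observed visits without imputation, in keeping with SAP 2.5. In either form the comparison rests on the fixed clinic visits, so a change in the monthly EQ-5D frequency would not alter it. Centre can be added but is not essential to this point. Report within-arm changes descriptively, without tests. As housekeeping, extend table 3.1.8 and listing 3.2.5 to AFEQT.

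The cost is a sentence in each document and one model per scale. No new data, visits or subjects are needed. The wording should be settled before outcome data are examined.

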## 7 **SELECTION, DISCONTINUATION, AND WITHDRAWAL OF SUBJECTS**

### 7.1 SELECTION CRITERIA

The criteria listed below shall be used to determine if a participant is eligible for entry into the study. A subject must meet ALL of the study inclusion criteria and NONE of the study exclusion criteria in order to be considered eligible for participation.

#### A. ***Inclusion Criteria***

Subjects are required to meet the following inclusion criteria:

1. Male or female 18 – 80 years of age.
2. Experiencing at least two (2) documented episodes of **paroxysmal** atrial fibrillation in the last 3 months preceding study entry with clinical indication for AF ablation per guidelines. At least one episode should be documented by rhythm strip or ECG.
3. Indicated for AF ablation according to current EHRA guidelines.
4. Prescribed with oral anticoagulation therapy, in indicated patients per the latest EHRA guidelines.
5. Willingness and able to remain on anti-coagulation therapy as per the latest EHRA guidelines.
6. Left atrial diameter < 5.5 cm as measured and image ((CT/TEE/TTE/ MRI or ICE) documented within previous six months up to pre-procedure.
7. Sustained AF (>5 min uninterrupted) during the electrophysiology procedure. If the subject is not experiencing spontaneous, sustained AF, it may be induced by burst pacing (typically from the coronary sinus) with or without isoproterenol infusion in conventional clinical fashion.
8. Willingness, ability and commitment to participate in baseline and follow-up evaluations.
9. Signed patient informed consent form.

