### B. *Baseline Assessment*

If the patient is not excluded on the basis of existing medical history and standard clinical work-up, the patient will be asked to provide informed consent to participate in the study. Baseline assessments include the following as shown in Table 5 – Schedule of Assessments.

- Determine study eligibility based on the requirements specified in the inclusion / exclusion criteria.
- Demographics.
- Medical history, including any hospitalizations or emergency room visits for episodes of all cardiac arrhythmias within six months of screening, all anti-arrhythmic drugs (AADs) and other cardiac medications.
- Reported incidence of at least two (2) documented episodes of symptomatic paroxysmal AF during the three months preceding trial entry (at least one episode should be documented by rhythm strip, CIED or ECG).
- Treatments administered for atrial fibrillation in the six months prior to enrollment, e.g., pharmacologic treatments and non-pharmacologic interventions. Medications should include dose and duration.
- Documentation of therapeutic International Normalization Ratio (INR) for three weeks prior to the procedure (if applicable per Inclusion Criteria) in cases of subjects taking warfarin.
- NYHA class.
- EHRA class.
- Current cardiac rhythm.
- Largest dimension left atrial diameter measured within the last 3 months or from transthoracic echo, cardiac CT or cardiac MR with image documentation. Intracardiac echocardiographic measurement at the time of the procedure can alternatively be used to document this.

- Ejection fraction (EF) measured within the last 3 months or from the pre-procedure TEE or TTE.
- When clinically indicated, TEE will be performed within 72 hours prior to the ablation procedure. If any evidence of left atrial thrombus is discovered, then the ablation procedure will not be performed at that time. The patient may be either excluded from the study or maintained on oral anticoagulation for an additional period of at least 6 weeks and re-tested (TEE repeated) for thrombi.
- If the patient has a preexisting CIED, interrogation of the device will be performed to document AF burden in the 1-2 months preceding the procedure.
- 12-Lead ECG within 72 hours of, or immediately prior to, study procedure.
- Cardiac medications currently prescribed for the subject's daily medical therapy.
- Laboratory values TSH, Electrolytes (sodium, potassium) and Creatinine

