### 15.2 STUDY ENDPOINTS

#### A. Long-Term Effectiveness (Primary effectiveness endpoint)

The primary effectiveness endpoint is single-procedure freedom from AF/AT recurrence from 3-12 months after the index AF ablation procedure (with 90-day blanking period).

The hypothesis to be tested is the recurrence rate for FIRM-guided AF ablation is not inferior to that experienced by the conventional AF ablation arm.

The statistical hypothesis for this endpoint is operationalized as follows:

$$H_0: \delta > .15$$

$$H_A: \delta < .15$$

$$\alpha = .05 \text{ (two-tailed)}$$

Where:

$$\delta = p_C - p_F$$

$p_C$  = Proportion free from AF recurrence at twelve (12) months post index ablation procedure for the conventional AF ablation arm (.50)

$p_F$  = Proportion free from AF recurrence at twelve (12) months post index ablation procedure for the FIRM-guided AF ablation arm (.55)

The non-inferiority margin for this hypothesis is 15% (.15). If the lower limit of the two-sided 95% confidence interval calculated for the difference in proportions ( $\delta$ ) is less than .15, the null hypothesis will be rejected and evidence in favor of the alternative (FIRM-guided ablation for atrial fibrillation is not inferior to conventional ablation for atrial fibrillation) affirmed.

This non-inferiority margin was chosen based on that used in the FreezeAF and VGLB trials.

 Luik, Armin MD, et. al. (2010). Rationale and design of the FreezeAF trial: A randomized controlled noninferiority trial comparing isolation of the pulmonary veins with the cryoballoon catheter versus open irrigated radiofrequency ablation in patients with paroxysmal atrial fibrillation. American Heart Journal. 159(4):555-560.

The proportion of successes in each treatment arm shall be estimated using Kaplan-Meier survival estimation.

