#### 15.3 POWER AND SAMPLE SIZE ESTIMATION

Since the primary objective of this study relates to the long-term effectiveness of FIRM-guided ablation versus conventional ablation for atrial fibrillation (AF), power and sample size estimates have been calculated relative to that endpoint only. We anticipate enrolling 77 subjects in each treatment arm, plus an additional 8 subjects per arm to account for possible drop-outs / lost to follow-ups, for a total of 170 subjects (in approximately 20 sites).

Description	Assumptions
FIRM Group Freedom from recurrence of AF at 3 months	.55
CONVENTIONAL Group Freedom from recurrence of AF at 3 months	.50
Probability of Type I error ( $\alpha$ ) (two-sided test)	.05
Minimum Total Sample Size (includes 10% adjustment for drop-outs and losses to follow-up)	170 (85 per group)

With 77 subjects in each group, the lower limit of the observed one-sided 95.0% confidence interval will be expected to exceed -0.150 with 80% power when the Standard proportion,  $p_c$ , is 0.500 and the Test expected proportion,  $p_F$ , is 0.550; results are based on 1000 simulations using the Newcombe-Wilson score method to construct the confidence interval. In order to account for potential drop-outs and losses to follow-up, an additional 10% (16) will be added to the total sample size, for a final sample size of 170 (85 per group).

This power and sample size calculation was performed using NQuery 7.0 on the Microsoft Windows 10 operating system.

---

 Newcombe RG (1988) Interval estimation for the difference between independent proportions: comparison of eleven methods. *Statistics in Medicine* 17:873-890.

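### Left atrial diameter is required of every eligible subject but not used in the primary comparison; if it predicts recurrence, adjusting for it would give a small, nearly free gain in precision

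*Protocol*

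**What the plan says.** **The covariate.** Protocol 7.1 requires subjects to meet all inclusion criteria. Criterion 6 is "Left atrial diameter < 5.5 cm as measured and image", by CT, TEE, TTE, MRI or ICE, within the previous six months. Protocol 9.1 B lists it again as a baseline item: "Largest dimension left atrial diameter measured within the last 3 months or from transthoracic echo, cardiac CT or cardiac MR with image documentation". That section adds an exception: "Intracardiac echocardiographic measurement at the time of the procedure can alternatively be used to document this". Age (18 to 80) is criterion 1 and should also be complete.

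**The primary analysis.** The endpoint in Protocol 15.2 A is "single-procedure freedom from AF/AT recurrence from 3-12 months after the index AF ablation procedure", with a 90-day blanking period. The estimator is stated in one sentence: "The proportion of successes in each treatment arm shall be estimated using Kaplan-Meier survival estimation". SAP 2.2.1 says the same. Neither names a baseline variable. The decision uses the "lower limit of the two-sided 95% confidence interval calculated for the difference in proportions" against a margin of 0.15.

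**Other relevant text.** The sample size in Protocol 15.3 and SAP 2.4 rests on an unadjusted Newcombe-Wilson interval. The only covariate in any long-term model is center, in a separate Cox model in SAP 2.6 that looks for site interaction. The table list in SAP 3.1 names no table of atrial size by arm.

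**The concern.** The primary verdict depends on one confidence limit clearing a 15-point margin, and at the planning rates the two-sided 95% half-width is itself nearly 16 points. With so little precision to spare, a baseline variable that is already collected on everyone is worth using if it explains part of the outcome. Adjustment narrows the interval without another patient or visit, and it takes any chance imbalance in that variable out of the estimate. The choice has to be made before the data are seen, because covariates picked afterwards would not be credible.

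**Working it through.** **Inputs from the documents.** Control 0.50, FIRM 0.55, margin 0.15, 77 evaluable per arm (Protocol 15.2 A and 15.3). Sizing uses a one-sided 95% limit: "the lower limit of the observed one-sided 95.0% confidence interval will be expected to exceed -0.150 with 80% power". The decision rule uses a two-sided 95% interval. In both cases I take the limit that bounds the FIRM deficit.

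**Assumed input.** r is the within-arm correlation of diameter with 12-month freedom. The documents do not give it, so I use 0 to 0.3. For scale, assumed odds ratios of 1.2, 1.5 and 2.0 per SD correspond to r² of about 0.008, 0.038 and 0.098.

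**Step 1: reproduce the plan's figure.**
- Distance from the expected difference to the margin: 0.05 + 0.15 = 0.20.
- Variance term: 0.50×0.50 + 0.55×0.45 = 0.4975.
- n = (1.645 + 0.842)² × 0.4975 / 0.20² = 77 per arm. Exact Newcombe-Wilson power at 77 is 80.6%. The stated 77 and 80% reproduce at one-sided 0.05.
- With 1.96 in place of 1.645, as the two-sided rule implies, n = 98 per arm, and power at 77 is about 70%.

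**Step 2: unadjusted precision at 77 per arm.** SE = sqrt(0.4975/77) = 0.0804. Half-width = 1.96 × 0.0804 = 0.1575.

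**Step 3: adjusted precision.** Adjusted SE = 0.0804 × sqrt(1 − r²). Power = Φ(0.20/SE − 1.96). Equivalent n = 77/(1 − r²).

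| r | Half-width | Narrowing | Power | Equivalent n per arm |
|---|---|---|---|---|
| 0 | 0.1575 | 0% | 70.1% | 77.0 |
| 0.1 | 0.1568 | 0.5% | 70.6% | 77.8 |
| 0.2 | 0.1543 | 2.0% | 71.9% | 80.2 |
| 0.3 | 0.1503 | 4.6% | 74.2% | 84.6 |

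At one-sided 0.05, the level used for sizing, r² = 0.10 moves power from 80.1% to 83.6%.

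**Step 4: chance imbalance.** The difference in mean diameter between arms has standard error sqrt(2/77) = 0.161 SD. With an outcome SD of about 0.5, an imbalance of 1.96 standard errors (0.316 SD) shifts the unadjusted difference by 0.5 × r × 0.316. That is 1.6, 3.2 or 4.7 points for r = 0.1, 0.2, 0.3.

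**Step 5: error rate and realised gain, by simulation.**
- Pseudo-value regression (1500 runs, 85 per arm, 10% censoring): non-inferiority declared at a true 15-point deficit in 1.9% to 2.6% of runs, against a nominal 2.5%. Power gain was about 0 to 2.5 points.
- Logistic standardisation (6000 runs), adjusted against unadjusted power: 0.710 and 0.711 at r = 0.1; 0.726 and 0.714 at r = 0.2; 0.740 and 0.702 at r = 0.3. Adjusted error at the margin was 2.2% to 2.8%.

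**The case against.** The strongest case against is that this is a matter of preference about a valid analysis, with a benefit that is assumed.

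- **The correlation is unknown and may be low.** This stands. The documents give no figure. The range is cut at 5.5 cm, several imaging methods are mixed, and the windows differ (six months in criterion 6, three months in 9.1 B). All of these push r down. At r = 0.1 the logistic simulation shows no visible gain.
- **The 5.5 cm cap does not show prognostic value.** This also stands. A reader might infer that the sponsor regards atrial size as a predictor of outcome, but criterion 6 gives no reason for the limit.
- **Chance imbalance is already covered.** This is correct on average over repeated trials, which is why a reader should not infer from Step 4 that the planned analysis is biased. Adjustment removes the imbalance from the single estimate that will be obtained; it does not repair an invalid one.
- **Some diameters may follow randomisation.** Protocol 7.4 places randomisation after the baseline assessments, while 9.1 B allows ICE at the procedure, when the operator may know the arm. This stands, and the fix needs a rule for it.
- **Center is the stratification factor and is left out.** Whether to add it is a fair question, but it does not bear on whether to use diameter. No gain from center, or from age, has been computed here.
- **Pseudo-values need censoring that does not depend on the covariates.** This is true. SAP 2.5 censors subjects with missing data at their latest prior visit, so the assumption should be stated.

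**Conclusion.** The point holds as a low-severity efficiency improvement. Diameter is required of every eligible subject and the primary comparison does not use it. On an assumed r of 0 to 0.3, the unadjusted interval is 0 to about 5% wider than necessary, worth at most about 8 subjects per arm (84.6 against 77) and about 4 power points (70.1% to 74.2%).

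Two stronger conclusions might be drawn, and the documents support neither. The first is that the planned interval is in fact too wide; that depends on a correlation the documents do not report, and at r = 0 nothing is lost. The second is that adjustment would restore the stated 80% power. The shortfall to about 70% comes from sizing on a one-sided 95% limit and deciding on a two-sided 95% interval, which is a separate matter. Even r² = 0.20, beyond the range assumed here, would reach only 79.4%.

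**What to change.** In Protocol 15.2 A and SAP 2.2.1, pre-specify as primary the marginal 12-month difference in freedom from AF/AT, adjusted for baseline left atrial diameter as a continuous variable and for age. One suitable method is to compute Kaplan-Meier pseudo-values at 12 months within each arm and regress them on arm, diameter and age, with an identity link and a robust standard error. The result is still a risk difference and is judged against the same 15-point margin.

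The SAP should also state:
- that the diameter used is the one recorded before randomisation where available, and otherwise the one recorded before ablation, with a simple rule for values first obtained at the procedure;
- the censoring assumption behind the pseudo-values;
- whether center enters the model;
- that the unadjusted Kaplan-Meier difference is reported as supportive, with diameter tabulated by arm.

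The cost is SAP and protocol wording and a few lines of code. No new data, visits or subjects are needed. If r proves to be near zero, almost nothing is lost by having adjusted.
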